5.3 SERIOUS ADVERSE EVENTS

All such events, whether expected or not, should be recorded.

An SAE form should be completed and faxed to the Chief Investigator within 24 hours. However, relapse and death due to Covid19, and hospitalisations for elective treatment of a pre-existing condition do not need reporting as SAEs.

All SAEs should be reported to the London South East Research Ethics Committee where in the opinion of the Chief Investigator, the event was:

- 'related', i.e. resulted from the administration of any of the research procedures; and
- 'unexpected', i.e. an event that is not listed in the protocol as an expected occurrence

Reports of related and unexpected SAEs should be submitted within 15 days of the Chief Investigator becoming aware of the event, using the NRES SAE form for non-IMP studies. The Chief Investigator must also notify the Sponsor of all SAEs.

Local investigators should report any SAEs as required by their Local Research Ethics Committee, Sponsor and/or Research & Development Office.

5.4 DATA SAFETY MONITORING COMMITTEE (DSMC)

A trial Data Safety Monitoring Committee (DSMC) will be formed to review the study after every 12 patients recruited to assess the progress, the safety data and the endpoints and to recommend to the sponsor whether to continue, modify or end the study.

Contact details for reporting SAEs

[contact]

CI email (and contact details below)

[contact]

Please send SAE forms to: London South East Research Ethics Committee

[contact] (Mon to Fri 09.00 – 17.00)

6. ASSESSMENT AND FOLLOW-UP

Incidental findings will be reviewed by the PI or designee and reported to the clinical team in charge of the patient if deemed clinically significant. The subject will be followed up for 24 hours after the dosing period has finished, and at day 30 at which point the subject will finish the study. There will be no further follow up. The definition of the end of trial is the last visit day of the last subject (Day 30).

7. STATISTICS AND DATA ANALYSIS

This sample size (30 each group) provides 80% power (alpha 0.05) to detect a 30% change in D-dimer. Subjects will be block randomised based on age (<60, 60-69, >69 years) using a code generated by the trial statistician.

Mean change from baseline D-dimer at day 1-3 post randomisation (and exploratory variables) will be compared using paired or unpaired non-parametric methods as appropriate. The relationship between change from baseline and pre-treatment plasma renin will be investigated, on the basis that subjects with low renin (and hence greater RAS activation) would be predicted to have the greater response.

The aim of this study is to understand the relationship between the RAS, coagulopathy, and COVID-19. The results of this study have potential implications for studies which are currently being planned using RAS modulators (including TRV027) in COVID-19. Design decisions for these study need to be taken before this study will fully recruit. Hence, unblinded aggregate data, for those patients who have completed the dosing period, will be reviewed by the study team to help guide the design of these studies. Individual unblinded data will not be reviewed.

Data and all appropriate documentation will be stored for a minimum of 10 years after the completion of the study, including the follow-up period.

8. REGULATORY ISSUES

8.1 ETHICS APPROVAL

The Study Coordination Centre has obtained approval from the London South East Research Ethics Committee (REC) and Health Regulator Authority (HRA). The study must also receive confirmation of capacity and capability from each participating NHS Trust before accepting participants into the study or any research activity is carried out. The study will be conducted in accordance with the recommendations for physicians involved in research on human subjects adopted by the 18th World Medical Assembly, Helsinki 1964 and later revisions.

8.2 CONSENT

Consent to enter the study must be sought from each participant only after a full explanation has been given, an approved participant information sheet provided and time allowed for consideration. Signed participant consent should be obtained before initiating any study procedures in patients that are capable of giving consent (refer to section 4.3 for further details). The right of the participant to refuse to participate without giving reasons must be respected. Participants that lack capacity may also be enrolled on the advice of a consultee (see section 4.3).

After the participant has entered the study the clinician remains free to give alternative treatment to that specified in the protocol at any stage if he/she feels it is in the participant's best interest, but the reasons for doing so should be recorded. In these cases the participants remain within the study for the purposes of follow-up and data analysis.

All participants are free to withdraw at any time from the protocol treatment without giving reasons and without prejudicing further treatment.

8.3 CONFIDENTIALITY

The Chief Investigator will preserve the confidentiality of participants taking part in the study and is registered under the Data Protection Act.

8.4 INDEMNITY

Imperial College London holds negligent harm and non-negligent harm insurance policies which apply to this study

8.5 SPONSOR

Imperial College London will act as the main Sponsor for this study. Delegated responsibilities will be assigned to the NHS trusts taking part in this study.

8.6 FUNDING

The study is funded by Imperial College London COVID-19 Fund, the British Heart Foundation and Trevena. Trevena is providing TRV027 and additional funds for pathology investigations, pharmacy costs, and study personnel support.

8.7 AUDITS

The study may be subject to inspection and audit by Imperial College London under their remit as sponsor and other regulatory bodies to ensure adherence to GCP and the UK Policy Frame Work for Health and Social Care Research.

8.8 COMPENSATION

Participants will not receive any payments, reimbursement of expenses or any other benefits or incentives for taking part in this research.

No individual researchers will receive any personal payment over and above normal salary, or any other benefits or incentives, for taking part in this research

9. STUDY MANAGEMENT

The day-to-day management of the study will be co-ordinated by the study project manager.

10. PUBLICATION POLICY

Data will be prepared for publication (open access) as soon as is practically possible at the end of the study. This could be through peer reviewed journals, internal reports and/or conference presentations.

Title: Investigating the relationship between the renin angiotensin system and the coagulopathy associated with COVID-19

Version 2.0 28th January 2021

MAIN SPONSOR: Imperial College London

FUNDERS: Trevena, Imperial College London, British Heart Foundation

[figure not shown]
STUDY COORDINATION CENTRE: NIHR ICRF

IRAS Project ID: 284196

REC reference: 20/HRA/3414

ClinicalTrials.gov ID: NCT04419610

Protocol authorised by:

Name & Role	Date	Signature
[name], Chief Investigator	13 May 2021	
[name], Statistician	13 May 2021	

Study Management Group

Chief Investigators: [name]

Co-investigators: [name], [name], [name]

Statistician: [name]

Study Management: [name]

Sponsor

Imperial College London is the main research Sponsor for this study. For further information regarding the sponsorship conditions, please contact the Head of Regulatory Compliance at:

Joint Research Compliance Office
Imperial College London and Imperial College Healthcare NHS Trust
[name]
[name]
[name]
[contact]
<http://www3.imperial.ac.uk/clinicalresearchgovernanceoffice>

Table of Contents

- 1. Background**
 - 1.1 Introduction**
 - 1.2 Study Objectives**
 - 1.3 Study Endpoints**
 - 1.4 Study Design and Population**
 - 1.5 Study Sample Size**
 - 1.6 Study Management**
- 2. General Considerations**
 - 2.1 General Considerations**
- 3. Analysis Plan**
 - 3.1 Descriptive Analysis**
 - 3.2 Efficacy Data**
 - 3.3 Exploratory Data**
 - 3.4 Safety Data**
 - 3.5 Drug Compliance**
 - 3.6 Mortality Data**
 - 3.7 Additional Data**

STUDY SUMMARY

TITLE Investigating the relationship between the renin angiotensin system and the coagulopathy associated with COVID-19

DESIGN Double blind randomised placebo-controlled trial

AIMS To determine whether RAS inhibition modulates coagulopathy in COVID-19

OUTCOME MEASURES D-dimer

POPULATION Inpatients with COVID-19

ELIGIBILITY Hospitalised, aged 18 or over

DURATION Each subject will be in the study for 30 days. The study is expected to take 6 months

1. INTRODUCTION

1.1 BACKGROUND

Several clinical trials testing blockade of Angiotensin II (AngII) in COVID-19 using angiotensin converting enzyme inhibitors (ACEI) or angiotensin II receptor blockers (ARBs) are underway (e.g. NCT04330300, NCT04335786 and NCT04355936). The rationale for these trials is based on the two predicates. First, SARS-CoV2 will lead to internalisation and inactivation of ACE2 (the enzyme that metabolises AngII to Ang(1-7)) and cause AngII accumulation, as occurred with SARS-CoV1 (Kuba, Lo, Gralinski, Wang). Second, that COVID-19 has many features which are strikingly similar to the effects of excessive exposure to AngII (Tang (a), Tang (b), Whitaker, Gavras (a), Gavras (b)). However, this approach may fail to yield net benefit, because it overlooks the role of Ang(1-7) and the impact of these drugs on Ang(1-7). Ang(1-7) is the product of ACE2 mediated AngII metabolism, and hence the inactivation of ACE2 induced by COVID-19 will lead not only to AngII accumulation, but also to Ang(1-7) depletion. Because this is due specifically to ACE2 inactivation, it does not occur in more classical conditions featuring renin-angiotensin axis activation, such as heart failure. Ang(1-7) functionally antagonises AngII through its agonist action at the MAS receptor, and may also potentially act as a biased agonist at the AngII receptor (AT1R) (Bader, Galandrin, Montezano, Teixeira, Touyz). Indeed, animal models show that Ang(1-7) depletion causes pathology which aligns with that seen in COVID-19 patients, including lung injury, lung inflammation, myocardial microinfarcts, characteristic glomerular thrombosis and coagulopathy. (Bihl, Bossi, Driggin, Fraga Silva, Hao, Klein, Supe, Xue, Yang (a), Yang (b), Zhang K, Zhang X).

The coagulopathy is particularly noteworthy given an early increase in D-dimer has very high positive predictor value for death in COVID-19, and D-dimer concentrations are unusually high in COVID-19, over and above what would be expected for an acute phase response in an unwell patient (Tang (a), Tang (b)). Given the pleiotropic effects of AngII and Ang(1-7) on the components of the coagulation system, overactivation of the renin angiotensin system may partly drive dysregulation of coagulation. We therefore hypothesise that the coagulopathy associated with COVID-19 is partly explained by both AngII accumulation and Ang(1-7) deficiency. Importantly, whilst ACEI and ARB treatment will antagonise AngII accumulation, they not only fail to address Ang(1-7) deficiency, but would in fact worsen it. This is because ACEI will further deplete Ang(1-7) production, over and above that caused by ACE2 internalization (Luque), and whilst an ARB will not further deplete Ang(1-7), it will prevent it from binding AT1R and hence block its beneficial actions via this receptor. Hence neither ACEI nor ARBs are appropriate tools to address this hypothesis in the context of COVID-19 infection

TRV027 is a similar peptide to Ang(1-7) but is a much more potent biased agonist at AT1R than Ang(1-7), potently and selectively recruiting β -arrestin to the AT1R while antagonizing Ang II-stimulated Gq activation (Violin). This β -arrestin bias of the ligand translates into unique downstream signaling, including extracellular signal-regulated kinases 1 and 2 (ERK1/2) phosphorylation and AT1R internalization. Recruitment of β -arrestin by TRV027 stimulates the activation of endothelial cell nitric oxide synthase (eNOS) and prostacyclin production (Violin). The combination of inhibition of Ang-II-mediated G-protein activation and activation of eNOS and prostacyclin production may contribute to the in vivo vasodilatory properties of TRV027 (Violin). ***In summary, TRV027, a biased agonist at AT1R, would be expected to oppose the effects of AngII accumulation, and functionally correct the Ang(1-7) deficiency.*** Hence it is an appropriate tool to examine the link between RAS activation and coagulopathy in the context of COVID-19 infection.

1.2 Study Objectives

Primary

To determine whether the coagulopathy associated with COVID-19 infection is driven by over activation of the renin angiotensin system (RAS)

Secondary objective

To investigate whether dysregulation of other systems associated with COVID-19 infection is driven by over activation of the renin angiotensin system (RAS)

1.3 Study Endpoints

Primary endpoint

Mean change from baseline D-dimer at day 1 to day 3 post randomisation will be compared using paired or unpaired non-parametric methods as appropriate.

Secondary endpoints

Mean change from baseline to day 1 plasma renin and from day 1 to day 3, day 5, day 8 for exploratory variables will be investigated

1.4 Study Design and Population

The study will be run as a double-blind, randomized controlled experimental medicine study in male and female hospitalised patients (n=60) aged 18 or over, with confirmed COVID-19 infection.

Patients who are admitted with confirmed COVID-19 infection will be screened with a routine medical assessment, and enrolled if they meet the eligibility criteria. Subjects will be block randomised based on age to continuous intravenous infusion of placebo or TRV027 for 7 days.

1.5 Study sample size

The sample size (30 each group) provides 80% power (alpha 0.05) to detect a 30% reduction in the D-dimer level. Subjects will be block randomised based on age (<60, 60-69, >69 years).

1.6 Study management

The day-to-day management of the study will be co-ordinated by the study project manager.

2. General Considerations

2.1 Analysis Strategy

Histograms and boxplots will be used to check the distribution and possible outliers for continuous variables. Continuous variables will be summarised using medians and ranges. Categorical variables will be summarised using frequencies and percentages.

2.2 Definition of population for analysis

The population for analysis will be the Full Analysis Set (FAS), which consists of all patients who received the full course of TRV027 or placebo. Patients who received at least 1 dose of TRV027 or placebo, but did not complete 3 days of infusion (Incomplete Analysis Set (IAS)) will be included in the baseline data set and summarised with descriptive statistics.

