2.5 Withdrawal from the study

Patients withdrawn from the study will still be included in the final analysis. Withdrawal can occur at any time according to the following reasons: Patient decision; toxicity, lost to follow-up; Death, or PI decision.

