3.6 Mortality data

Patient survival status will be monitored up to day 30 and tabulated in Table 9.

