3.7 Additional data

Vital signs and cardiovascular monitoring will be documented at days 1, 3 and 5. (Table 12).

Table 1. Baseline characteristics

	FAS		IAS	
	Control	TRV027	Control	TRV027
	Median (range) or N (%)			
Age (yr)				
Age group				
<60				
60-69				
>69				
Gender				
Male				
Female				
BMI (kg/m²)				
Ethnicity				
White				
Mixed				
Asian				
Black				
Other				
Disease severity?				
Ie FDA grade 1-5?				

Table 2 Drug Compliance

	Control N (%)	TRV027 N (%)
Total Missed doses		
Total % Compliance		
Median missed doses per patient (range)		
Patients with missed dose due to hospital discharge		
Patients with missed dose due to death		

Table 3 Safety data – Pooled Adverse events

	Control		TRV-027	
	No. of Events	No. of Subjects*	No. of Events	No. of Subjects*
Number of Adverse events				
Severity				
Grade 1				
Grade 2				
Grade 3				
Grade 4				
Grade 5				
Missing				
AE classification				
Not serious				
Serious				
AE expectedness				
Expected				
Unexpected				
Not Applicable				
Missing				
Relation to study				
Definitely				
Probably				
Possibly				
Unlikely				
Not related				
Not assessable				
Missing				

* A patient may have several AEs

Table 4 – TRV027 Safety data –Adverse events details by patient

Control				TRV-027			
Pt ID	AE category	AE name	Grade	Pt ID	AE category	AE name	Grade

Table 6 Safety data – Serious Adverse Events

	Control		TRV027	
	No. of Events	No. of Subjects	No. of Events	No. of Subjects
Number of Serious Adverse Events				
Reasons for SAE				
Resulted in death				
Life threatening				
Congenital anomaly/birth defect				
Persistent or significant				
Disability/incapacity				
Inpatient hospitalisation/prolongation of existing				
Other				
Severity				
Mild				
Moderate				
Severe				
Life threatening				
Death				
Causal relationship to study drug				
Definitely				
Probably				
Possibly				
Unlikely				
Not related				
Not assessable				

Table 7 Safety data – Serious Adverse events details (Controls)

SAE description	SAE Term	Outcome

Table 8 Safety data – Serious Adverse events details (TRV027)

SAE description	SAE Term	Outcome

Table 9 Day 30 Survival

	Control	TRV027
Alive		
Dead		
Lost to follow-up		

Table 10 FAS Efficacy and exploratory parameters

	Control			TRV027		
	Day 1 [N=] Median (range)	Day 3 [N=] Median (range)	Difference D3 – D1	Day 1 [N=] Median (range)	Day 3 [N=] Median (range)	Difference D3 – D1
D-dimer						
Platelets						
aPTT						
INR						
Fibrinogen						

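### SAP 2.2 names a completers-only set as the single analysis population and defines no safety or as-randomised set, so the adverse-event, SAE and Day 30 survival tables can lose patients who stop early or die during infusion

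*SAP*

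**What the plan says.** SAP 2.2 defines two sets. The first is the FAS: "The population for analysis will be the Full Analysis Set (FAS), which consists of all patients who received the full course" of either treatment. The second is the IAS, for patients who had at least one dose but "did not complete 3 days of infusion (Incomplete Analysis Set (IAS)) will be included in the baseline data set and summarised with descriptive statistics". The SAP defines no other set.

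The sections that plan the safety and survival output name no population. SAP 3.4 covers adverse events and SAEs and promises details for every SAE. SAP 3.6 says "Patient survival status will be monitored up to day 30 and tabulated in Table 9".

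SAP 2.5 bears on the same patients: "Patients withdrawn from the study will still be included in the final analysis". Its list of withdrawal reasons includes toxicity and death. Table 2 has a row headed "Patients with missed dose due to death".

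The length of a full course is not defined. SAP 1.4 says "Subjects will be block randomised based on age to continuous intravenous infusion of placebo or TRV027 for 7 days", whereas SAP 3.5 counts 72 hours as complete dosing, but only for the primary endpoint.

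**The concern.** This point is about the safety and survival tables only, whatever set is used for D-dimer. A safety table should include everyone exposed to the infusion, and a survival table everyone randomised. If entry to either depends on finishing the infusion, a patient stopped for toxicity can be missing from the table meant to show that toxicity, and Day 30 survival becomes survival among completers.

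The affected group may not be small. Protocol 4.4 expects many patients to progress to organ failure, with intensive-care admission or death. Protocol 5.3 says COVID-19 deaths need not be reported as SAEs, and Protocol 5.2 ends adverse-event recording 24 hours after the infusion. Table 9 is therefore the one shell designed to count every death to Day 30. Protocol section 7 also says the results may inform other studies of RAS modulators, TRV027 included.

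**Working it through.** **Step 1. Which population governs each table?**

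| Output | Population named in the SAP |
|---|---|
| Table 1, baseline | FAS and IAS columns |
| Table 2, compliance | none |
| Tables 3-8, AEs and SAEs (3.4) | none |
| Table 9, Day 30 survival (3.6) | none |
| Table 10, D-dimer and laboratory | FAS, in the title |
| Table 12, vital signs | none, and no arm columns |

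Where a table names no population, the general rule in 2.2 is the only definition available, and that rule is the FAS.

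**Step 2. Which patients does 2.2 leave out?** This depends on the meaning of full course.

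| Infusion received | If 72 hours (3.5) | If 7 days (1.4) |
|---|---|---|
| Started, under 3 days | IAS | IAS |
| 3 to under 7 days | FAS | neither set |
| 7 days | FAS | FAS |

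On the 72-hour reading, the FAS loses patients who stop or die before 72 hours. On the 7-day reading, it loses everyone who stops before the 7 days are complete, including patients discharged early. Those with 3 to under 7 days then belong to no defined set.

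**Step 3. Does 2.2 agree with the rest of the SAP?** Under 2.5, a patient withdrawn for toxicity or death stays in the final analysis. Under 2.2, the same patient is outside the population for analysis. Both cannot be followed. The Table 2 row on deaths also presupposes patients who did not complete. If compliance and the FAS use the same definition of a course, FAS patients alone could never fill that row.

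**Step 4. Effect on a survival table.** The documents give no mortality or discontinuation rate, so there is no planned figure to reproduce. The only input taken from them is 30 per group (SAP 1.5). Every other count below is assumed.

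Let n be patients per arm, d deaths by Day 30, e those deaths among patients who did not complete, and s survivors who did not complete.

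- All patients: d / n
- Completers only: (d - e) / (n - e - s)

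*Shrinkage.* TRV027 d = 8, e = 4, s = 0; control d = 4, e = 0, s = 0.
- All patients: 8/30 = 26.7% v 4/30 = 13.3%, a difference of 13.3 points.
- Completers: (8 - 4)/(30 - 4) = 4/26 = 15.4% v 4/30 = 13.3%, a difference of 2.1 points.

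*Reversal.* TRV027 d = 6, e = 5; control d = 3, e = 1; s = 0 in both.
- All patients: 6/30 = 20.0% v 3/30 = 10.0%.
- Completers: 1/25 = 4.0% v 2/29 = 6.9%.

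*Opposite direction, 7-day reading.* An arm with d = 4, e = 0 and s = 6 survivors discharged early.
- All patients: 4/30 = 13.3%.
- Completers: 4/(30 - 6) = 4/24 = 16.7%.

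*Sensitivity to timing.* With d = 6 of 30 (20.0%) and s = 0, completer mortality is 5/29 = 17.2%, 3/27 = 11.1% or 1/25 = 4.0% when e is 1, 3 or 5.

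*Patients omitted.* If 10%, 20% or 30% of each arm do not complete, a completers-only table leaves out 6, 12 or 18 of 60.

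**The case against.** The strongest reply is that the SAP does not mean to restrict these tables. Only Table 10 has FAS in its title, a label that would be redundant if the FAS governed everything. SAP 3.4 promises details of every SAE, 2.5 keeps withdrawals in, and 3.6 speaks of patient survival without limit. The IAS sentence also says those patients "will be included in the baseline data set and summarised with descriptive statistics"; Tables 2-9 are descriptive, so it could be read to cover them. On the 72-hour reading, FAS and IAS together cover every dosed patient. Safety oversight during the trial does not rest on these tables, because Protocol 5.4 has a monitoring committee review safety data after every 12 patients. The primary endpoint is D-dimer, and survival and adverse events are not listed endpoints.

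Much of this stands. A reader might infer that the plan deliberately drops early stoppers and deaths, so that they appear in no adverse-event, SAE or survival count. The documents do not support that, given 2.5, 3.4, the unlabelled tables and the Table 2 row. Nor does the SAP say that IAS patients appear only at baseline.

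What does not stand is the idea that the gap is therefore closed. Nowhere does the SAP say that Tables 2-9 and 12 are unrestricted. The IAS sentence mentions baseline and no safety output, and only Table 1 has IAS columns. The 72-hour figure is stated for the primary endpoint alone. Committee review during the trial does not define the final tables.

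**Conclusion.** The point holds as a fault in a stated rule that conflicts with other parts of the same document. SAP 2.2 makes completion the condition for analysis and provides no safety or as-randomised set. Followed literally, it makes the safety and survival tables depend on tolerating and surviving the infusion.

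The size cannot be fixed from the documents. It depends on the meaning of full course, on how many patients stop or die before completing, and on how these are split between arms. The shrinkage and reversal examples use deliberately unequal timing of deaths between arms and show what is possible, not what is expected.

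A reader might also infer that the bias always runs towards no difference or always hides harm. That does not follow. On the 7-day reading, survivors discharged early leave the denominator too, which raises completer mortality, so the bias can go either way. Sample size and power are unaffected.

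**What to change.** In SAP 2.2:

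- Define a Safety Set of every patient in whom infusion was started, by treatment received, and assign Tables 2-8 and 12 to it. Add arm columns to Table 12, which has none.
- Base Table 9 on all randomised patients by allocated arm. An all-dosed survival table would also remove the dependence on completion, but the as-randomised set keeps the comparison that randomisation protects. Table 9 already has a row for loss to follow-up.
- State that FAS and IAS do not restrict these tables, though they may be shown as sub-columns as in Table 1.
- Print N in each table header.
- Reconcile 2.2 with 2.5 and 3.5 on what full course means, so that every dosed patient falls into a defined set.

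The cost is a few lines of SAP wording and some table headers. No new data are needed: Protocol 5.2 already records adverse events until 24 hours after the infusion ends, Protocol section 3 plans monitoring after an early stop, and status is checked at Day 30.

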3. STUDY DESIGN

The proposed study will be run as a double-blind, randomized controlled experimental medicine study in male and female hospitalised patients (n=60) aged 18 or over, with confirmed COVID-19 infection. Patients who are admitted with confirmed COVID-19 infection will be screened with a routine medical assessment (see Table 1) and enrolled if they meet the eligibility criteria. Subjects will be block randomised based on age to continuous intravenous infusion of placebo or TRV027 for 7 days.

Day 1 procedures can occur on the same day of screening and include a venous blood test prior to commencing an intravenous infusion of either placebo (250ml sodium chloride 0.9%) or TRV027 in 250ml sodium chloride 0.9% at 12mg/hr. The infusions will continue for 7 days. Venous blood tests will be repeated at days 3, 5 and 8 amounting to approximately 120mLs of blood in total over the 8-day period.

Once the infusion has finished, the subjects will remain in hospital for a further 24 hours for vital signs and adverse event monitoring. If the infusion is stopped before the 7-day dosing period finishes, they will be advised to remain in hospital for a 24-hour period for monitoring during which time the study assessments will continue. If discharge is planned for day 6 or 7 the day 8 blood tests can be taken on the day of discharge. They will also be followed up at Day 30 either by telephone call or through examination of medical records.

Table 1: Schedule of Study Events

Study Day	*Screening	*1	2	3	4	5	6	7	8	9	30
Informed consent (or agreement from consultee if incapacitated)	X										
Eligibility assessment; routine medical assessment (history, observations)	X										
Review of Concomitant Medications ¹		X	X	X	X	X	X	X	X		
Pregnancy test (If appropriate)	X										
Venous blood test for primary and exploratory endpoint assessment:											
D-dimer		X		X		X			X		
Platelets		X		X		X			X		
aPTT		X		X		X			X		
INR		X		X		X			X		
Fibrinogen		X		X		X			X		
Plasma Renin Mass		X									
Total Bilirubin		X		X		X			X		
LDH		X		X		X			X		
Haptoglobin		X		X		X			X		
Creatinine		X		X		X			X		
BNP		X		X		X			X		
Troponin		X		X		X			X		
Ferritin		X		X		X			X		
Pro-calcitonin		X		X		X			X		
Glucose		X		X		X			X		
Clinical assessment for exploratory endpoints											
Inotrope requirement		X		X		X			X		
GCS		X		X		X			X		
SOFA score		X		X		X			X		
Randomisation		X									
Infusion		X	X	X	X	X	X	X	X		
Vital signs monitoring four times a day		X	X	X	X	X	X	X	X	X	

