3.5 Drug Compliance

Drug compliance will be determined using data entered on to Redcap to calculate patient drug compliance. Number and duration of dose interruptions will be reported for each patient and compliance reported as the percentage of dose completion (Table 2). Although patients may receive up to 7 days infusion, for the primary endpoint, 72hrs infusion will be considered 100%.

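### The SAP's only efficacy population is restricted to patients who completed an undefined full course, and no as-randomised comparison is planned

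*SAP*

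**What the plan says.** SAP 2.2 makes the Full Analysis Set (FAS) the population for analysis, "which consists of all patients who received the full course of TRV027 or placebo". Patients who were dosed but had under 3 days of infusion form an Incomplete Analysis Set (IAS), which receives baseline and descriptive summaries only. Patients randomised but never infused are in neither set. The efficacy shell is headed "Table 10 FAS Efficacy and exploratory parameters", and the baseline shell (Table 1) has columns for FAS and IAS alone.

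The length of a full course is not stated in SAP 2.2. SAP 1.4 and protocol section 3 plan a 7-day infusion. SAP 3.5 says that "for the primary endpoint, 72hrs infusion will be considered 100" per cent compliance. Protocol section 3 foresees early discharge: "If discharge is planned for day 6 or 7 the day 8 blood tests can be taken on the day of discharge".

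Two other passages govern who is analysed. SAP 2.5: "Patients withdrawn from the study will still be included in the final analysis", with toxicity and death among the listed reasons for withdrawal. Protocol 8.2, on patients whose clinician gives alternative treatment: "In these cases the participants remain within the study for the purposes of follow-up and data analysis".

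On numbers, SAP 1.4 has "hospitalised patients (n=60) aged 18 or over" and SAP 1.5 states: "The sample size (30 each group) provides 80% power (alpha 0.05"). Neither section says whether 30 per group is randomised or evaluable, and no allowance for exclusions is visible.

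**The concern.** Completing the infusion happens after randomisation and may depend on both treatment and clinical course. A comparison restricted to completers therefore lacks the protection that randomisation gives.

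The documents themselves suggest that non-completion will be related to outcome. Protocol 4.4 expects many patients to progress to intensive care or death. SAP Table 2 has rows for doses missed through discharge and through death. Protocol 1.1 describes an early rise in D-dimer as strongly predictive of death. Patients doing badly and patients doing well can both leave the set, so the bias could run either way.

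The name Full Analysis Set would also mislead a reader about who was analysed. An undefined full course leaves the population open to choice after the data are seen.

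**Working it through.** **The two readings of full course**

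| | 7 days (SAP 1.4) | 72 hours (SAP 3.5; IAS cut-off in SAP 2.2) |
|---|---|---|
| Under 3 days of infusion | IAS, no efficacy comparison | IAS, no efficacy comparison |
| 3 to under 7 days | In neither set, and absent from Table 1 | In the FAS |
| 7 days | FAS | FAS |
| Never infused | In neither set | In neither set |

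On the 7-day reading, a patient can have both D-dimer samples for the primary endpoint and appear in no set. On the 72-hour reading only those stopping before 72 hours are dropped. The documents give no clock time for the Day 3 sample. An infusion starting on Day 1 reaches 48 hours on Day 3 and 72 hours on Day 4, so this reading may also drop patients whose primary endpoint is already measured. Protocol section 3 continues study assessments for 24 hours after an early stop, so some of these data will exist.

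Both readings conflict with SAP 2.5 for patients withdrawn before completing the course. Both conflict with protocol 8.2 where alternative treatment ends the infusion early.

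**Power**

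The plan gives no SD or scale, so its 80% cannot be reproduced directly. The implied effect can be solved for. With 30 per arm, two-sided alpha 0.05 (sidedness assumed) and 80% power, the noncentral t gives a standardised effect d = 0.7356. If the 30% reduction is on the log scale, the implied SD of log-change is −ln(0.7)/0.7356 = 0.3567/0.7356 = 0.485.

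Holding d fixed and taking 30 as randomised (loss rates are assumptions):

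| Excluded per arm | n per arm | Power | Randomised per arm to keep 30, 30/(1−p) |
|---|---|---|---|
| 10% | 27 | 75.6% | 34 |
| 20% | 24 | 70.4% | 38 |
| 30% | 21 | 64.3% | 43 |

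**Bias with no true effect**

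Suppose the worst share p of each arm, on a variable correlated ρ with log-change, is excluded. The spurious log difference is −ρ × SD × [h(p_TRV027) − h(p_placebo)], where h(p) = φ(z)/(1−p) and z is the upper-p normal quantile. This gives h(0.05) = 0.109, h(0.10) = 0.195, h(0.20) = 0.350 and h(0.30) = 0.497. Losing improvers reverses the sign.

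Worked case, 30% v 10% and ρ = 0.7: 0.7 × 0.485 × (0.497 − 0.195) = 0.1025. That is a spurious reduction of 1 − exp(−0.1025) = 9.7% if worseners leave, or an increase of exp(0.1025) − 1 = 10.8% if improvers leave.

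Over ρ = 0.5 to 0.7, with type I error from 40,000 simulated trials per scenario (pooled t-test):

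| Loss, TRV027 v placebo | Spurious effect | Type I error |
|---|---|---|
| Equal 10% or 20%, same reason | none | about 5% |
| Worseners, 10% v 5% | 2.1–2.9% reduction | about 5–6% |
| Worseners, 20–30% v 10% | 3.7–9.7% reduction | about 6–12% |
| Improvers, 20–30% v 10% | 3.8–10.8% increase | about 6–12% |

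**Cost of keeping early stoppers**

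If a share p of TRV027 patients stop early and keep a fraction k of the effect, d becomes 0.7356 × (1 − p + pk), with all 30 per arm analysed.

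| p | k = 0 | k = 0.5 | Completers only, same p excluded from each arm |
|---|---|---|---|
| 10% | 71.3% | 75.9% | 75.6% |
| 20% | 61.1% | 71.3% | 70.4% |

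These allow for dilution of the mean only. Adding the extra variance of the mixture takes 61.1% to 59.3%.

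**The case against.** **The 72-hour reading is the more coherent one.** SAP 2.2 sets incompleteness at under 3 days, SAP 3.5 counts 72 hours as complete for the primary endpoint, and Table 1 covers every dosed patient only on that reading. This stands as a matter of likelihood. But SAP 3.5 is a compliance rule that the FAS definition does not adopt, and patients stopping before 72 hours are excluded either way.

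**The conflicts are narrower than they look.** Protocol 8.2 is breached only where alternative treatment ends the infusion early. SAP 2.5 refers to the final analysis, and early withdrawals do appear in baseline and descriptive summaries. Both points stand. The remaining contradiction concerns early withdrawals in the efficacy comparison, which is where it matters.

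**The harm is assumed.** The documents give no non-completion rate. Protocol 1.3 reports one discontinuation for hypotension in a 33-patient study, but no difference from placebo in discontinuations or deaths among 621 heart failure patients. Equal loss for the same reason does no damage, and the largest figures need threefold differential loss with a correlation of 0.7. The simulation uses a t-test, while the protocol names non-parametric methods and SAP 3.2 leaves the choice open. All this stands, so the case rests on the selection rule and the contradiction, not on a particular bias figure.

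**The aim is mechanistic, and keeping early stoppers can cost power.** Both are true. They justify keeping a completer analysis as support, not as the only comparison.

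**The remedy is itself an available-case set.** With no imputation (SAP 2.4), patients without a Day 3 value leave the primary comparison under either rule. That also stands, and is why those patients must be reported by arm.

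**Conclusion.** The concern holds and must be fixed. Followed as written, the primary comparison is restricted to patients selected on a post-randomisation event, no as-randomised comparison supports it, and SAP 2.2 contradicts SAP 2.5 and, where treatment is changed early, protocol 8.2. None of this depends on which meaning of full course is adopted.

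The size and direction of bias are undetermined. The calculations show a range from none to a spurious change of about 10% in D-dimer with type I error near 12%, on assumed loss rates, correlations of 0.5–0.7 and a log-scale SD back-calculated from the plan's power statement. The power loss applies only if 30 per group means randomised.

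**What to change.** - **SAP 2.2:** define the primary set as all randomised patients who started the blinded infusion, analysed in the randomised arm, using everyone with a baseline and a Day 3 D-dimer whatever infusion they received.
- **Completer set:** keep it, under one stated definition of completion, as a labelled per-protocol sensitivity analysis. It suits the mechanistic aim.
- **Exclusions:** report by arm and reason the patients never infused and those with no Day 3 value. Add a sensitivity analysis ranking deaths before Day 3 as the worst outcome, since those patients cannot enter the primary comparison.
- **Consistency:** reconcile SAP 2.2, 2.5 and 3.5 with each other and with protocol 8.2, and relabel Tables 1 and 10 to match. Which infusion length counts as complete is for the sponsor to settle.
- **SAP 1.5:** state whether 30 per group is randomised or evaluable, and restate power for the number expected to be analysed.

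The cost is SAP wording, table shells and two sensitivity runs, with no new patients or data. The statistical price is dilution from early stoppers, which is not always slight: with 20% of TRV027 patients stopping and keeping no effect, power falls below that of the completers-only analysis. The restated power should show this.
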